6.12 Correlative Research

A mandatory correlative research component is part of this study, the patient will be automatically registered onto this component (see Sections 3.19e and 14.0).

- 6.13 Documentation of IRB approval must be on file in the Registration Office before an investigator may register any patients.

In addition to submitting initial IRB approval documents, ongoing IRB approval documentation must be on file (no less than annually) at the Registration Office (fax: [REDACTED]). If the necessary documentation is not submitted in advance of attempting patient registration, the registration will not be accepted and the patient may not be enrolled in the protocol until the situation is resolved.

When the study has been permanently closed to patient enrollment, submission of annual IRB approvals to the Registration Office is no longer necessary.

- 6.14 Prior to accepting the registration, the registration/randomization application will verify the following:
- IRB approval at the registering institution
 - Patient eligibility
 - Existence of a signed consent form
 - Existence of a signed authorization for use and disclosure of protected health information
- 6.15 At the time of registration, the following will be recorded:
- Patient has/has not given permission to store and use his/her sample(s) for future research of CLL at Mayo.
 - Patient has/has not given permission to store and use his/her sample(s) for future research to learn, prevent, or treat other health problems.
 - Patient has/has not given permission for MCCC to give his/her sample(s) to researchers at other institutions.
- 6.16 Treatment on this protocol must commence at Mayo Clinic Rochester, Mayo Clinic Arizona, or Mayo Clinic Florida institution under the supervision of a medical oncologist or hematologist.
- 6.17 Treatment cannot begin prior to registration and must begin ≤ 21 days after registration.
- 6.18 Pretreatment tests/procedures (see Section 4.0) must be completed within the guidelines specified on the test schedule.
- 6.19a All required baseline symptoms (see Section 10.6) must be documented and graded.
- 6.19b Study drug (Pevnar 13®) is available on site.
- 6.2 Randomization Procedures
- 6.21 The factors defined in Section 5.0, together with the registering membership, will be used as stratification factors.
- 6.22 After the patient has been registered into the study, the values of the stratification factors will be recorded, and the patient will be assigned to one of the following treatment groups using the Pocock and Simon dynamic allocation procedure which balances the marginal distributions of the stratification factors between the treatment groups (35).
- Arm A (lenalidomide + Pevnar 13®)
 - Arm B (Pevnar 13®)

7.0 Protocol Treatment

7.1 Treatment Schedule

Arm	Agent	Dose Level	Route	Day
A	lenalidomide	2.5 mg	Oral	1-14
	lenalidomide	5 mg*	Oral	15-42
	Aspirin	325 mg	Oral	1-42
	Plevnar 13®**	1 dose	IM	15
B	Plevnar 13®**	1 dose	IM	15

* Unless dose reduced for adverse events, see Section 8.0

** Plevnar 13® vaccination should be administered on day 15 regardless of lenalidomide toxicity unless treating physician determines it should be held. If Plevnar 13® held, it should be administered as soon as deemed appropriate by treating physician.

7.2 For this protocol, the patient must return to the consenting institution for evaluation on Day 15 (+/-3 days) and Day 43 (+/-4 days) of the study.

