 - Weight loss $\geq 10\%$ within the previous 6 months
 - Extreme fatigue attributed to CLL
 - Fevers $>100.4^\circ\text{F}$ for 2 weeks without evidence of infection
 - Drenching night sweats without evidence of infection
- Note:
1. Prior chemotherapy or monoclonal antibody based therapy for treatment of CLL or SLL will be considered prior therapy. Nutraceutical treatments with no established benefit in CLL (such as epigallocatechin gallate or EGCG, found in green tea or other herbal treatments) will not be considered “prior treatment”.
 2. Prior corticosteroid therapy for an indication other than CLL/SLL will not be considered “prior treatment”. Previous use of corticosteroids for treatment of autoimmune complications of CLL/SLL does not constitute prior therapy for CLL/SLL.
- 3.15 Age ≥ 18 years.
- 3.16 ECOG Performance Status (PS) 0 or 1 (Appendix III).

- 3.17 The following laboratory values obtained ≤ 14 days prior to registration.
- Absolute neutrophil count (ANC) $\geq 1000/\text{mm}^3$
 - Platelet count $\geq 100,000/\text{mm}^3$
 - Hemoglobin ≥ 11.0 g/dL
 - Total bilirubin ≤ 1.5 x upper limit of normal (ULN) unless due to Gilbert's disease. If total bilirubin is >1.5 x ULN, a direct bilirubin should be performed and must be <1.5 mg/dL for Gilbert's to be diagnosed.
 - Aspartate transaminase (AST) ≤ 3 x ULN
 - Calculated creatinine clearance must be ≥ 50 ml/min using the Cockcroft-Gault formula below:

Cockcroft-Gault Equation:

$$\text{Creatinine clearance for males} = \frac{(140 - \text{age})(\text{weight in kg})}{(72)(\text{serum creatinine in mg/dL})}$$

$$\text{Creatinine clearance for females} = \frac{(140 - \text{age})(\text{weight in kg})(0.85)}{(72)(\text{serum creatinine in mg/dL})}$$

- 3.18 Provide informed written consent.
- 3.19a Willing to return to enrolling institution for follow-up (during the Active Monitoring Phase of the study).
- 3.19b All study participants must be willing to be registered into the mandatory Revlimid REMS® program, and be willing and able to comply with the requirements of the REMS® program. NOTE: Actual registration in the Revlimid REMS® program may occur after the patient is randomized since this requirement only applies to patients randomized to Arm A.
- 3.19c Females of reproductive potential must be willing to adhere to the scheduled pregnancy testing as required in the Revlimid REMS® program. NOTE: This requirement only applies to patients randomized to Arm A.

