4.0 Test Schedule

Tests & Procedures	Active Monitoring Phase				
	Days Prior to Registration	Day 15 (+/- 3 days)	Day 28 (+/- 7 days)	Day 43 (+/- 4 days)	Observation: 28 days after end of first cycle (Day 72 +/- 10 days)
	≤14 days				
Medical history	X				
Adverse event assessment	X	X		X	X
Physical exam, including PS, weight and vital signs	X			X	X
Height	X				
Register in the REVLIMID REMS® program (Arm A only)	X ⁸				
Counseling for the REVLIMID REMS® program (Arm A only)			X		
Tumor measurement by physical exam	X ¹			X ¹	
Peripheral blood immunophenotyping by flow cytometry	X ²				
CBC with differential and reticulocytes	X	X		X	X
Serum pregnancy test	X ³	X ³	X ³	X ³	
Chemistry group (SGOT [AST], SGPT [ALT], total bilirubin, serum creatinine, calcium, alkaline phosphatase, uric acid, LDH, potassium)	X	X		X	
Glucose	X				
Direct bilirubin	X ⁷				
CD38	X ²				
ZAP-70	X ²				
IGHV	X ⁴				
CD49d	X ⁴				
Serum protein electrophoresis	X			X	
Beta-2-microglobulin	X				
Peripheral blood CLL FISH panel	X ⁶				
Serum quantitative immunoglobulins (IgG, IgA, IgM)	X			X	
Coombs test (monospecific direct coombs IgG and C3)	X				
EKG	X				
Quantitative T & B cells, peripheral blood	X			X	

Prevna 13 pneumococcal vaccination		X			
Research blood specimens (see Section 14.0)	X ^{5,R}	X ^{5,R}		X ^{5,R}	

1. Physical exam should measure the spleen and liver noting the maximal distance below the respective costal margins and should record the bidimensional diameter of the largest palpable node in each area of involvement including the following sites: left neck (sub-mandibular, cervical, supra-clavicular), right neck (sub-mandibular, cervical, supra-clavicular), left axillary, right axillary, left groin (inguinal, femoral) and right groin (inguinal, femoral).
 2. May be waived for patients who have previously had full flow immunophenotyping consistent with CLL performed at Mayo Clinic. Similarly, if the patient has previously had CD38 and/or ZAP-70 testing performed at Mayo Clinic, repeat assay is elective after discussing with the study chair.
 3. For women of childbearing potential only. Must follow pregnancy testing requirements as outlined in the Revlimid REMS® program material.
 4. If patient has previously had done clinically at Mayo Clinic, this does not need to be repeated.
 5. Blood specimens will be collected and submitted at baseline, Day 15 and Day 43. Kits are required.

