8.0 Dosage Modification Based on Adverse Events

Strictly follow the modifications in this table. If multiple adverse events are seen, administer dose based on greatest reduction required for any single adverse event observed.

ALERT: *ADR reporting may be required for some adverse events (See Section 10)*

8.1 ARM A: Dose Levels (Based on Adverse Events in Tables 8.2).

Dose Level	Lenalidomide Days 1-14	Lenalidomide Days 15-42
0	2.5 mg p.o. once daily	5 mg p.o once daily
-1	2.5 mg p.o. every other day	2.5 mg p.o. once daily
-2	2.5 mg p.o. Mondays and Thursdays	2.5 mg p.o. every other day

* Dose level 0 refers to the starting dose.

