8.2 Lenalidomide Dose Modifications

→ → Use the NCI Common Terminology Criteria for Adverse Events (CTCAE) version 4.0* unless otherwise specified ← ←			
CTCAE System/Organ/Class (SOC)	ADVERSE EVENT	AGENT	ACTION
Days 1-42			
Blood and lymphatic system disorders	Anemia ≥ Grade 3		Transfuse red blood cells at physician discretion. Continue current dose level. For repeat episodes of anemia related to lenalidomide, dose may be reduced at physician's discretion.
	Anemia ≤ Grade 2		Transfuse red blood cells at physician discretion. Continue current dose level.
Cardiac disorders	Sinus bradycardia or Ventricular arrhythmia Grade 2		Omit lenalidomide (interrupt dose). Re-evaluate toxicity weekly. When symptoms resolve to ≤grade 1, decrease lenalidomide by 1 dose level and restart lenalidomide at the discretion of the treating physician. If symptoms do not resolve to ≤grade 1 by Day 35, discontinue lenalidomide treatment.
	Sinus bradycardia or Ventricular arrhythmia ≥Grade 3		Discontinue lenalidomide treatment.
Endocrine disorders	Hyperthyroidism ≥ Grade 2		Omit lenalidomide (interrupt dose). Initiate appropriate therapy. Reassess in 2 weeks. If symptoms resolve to ≤grade 1 decrease lenalidomide by 1 dose level and resume treatment. If symptoms do not resolve to ≤grade 1 by Day 35, discontinue lenalidomide.
	Hypothyroidism ≥ Grade 2		Omit lenalidomide (interrupt dose). Initiate appropriate therapy for hypothyroidism. Reassess in 2 weeks. If symptoms resolve to ≤grade 1 decrease lenalidomide by 1 dose level and resume treatment. If symptoms do not resolve to ≤grade 1 by Day 35, discontinue lenalidomide.

→ → Use the NCI Common Terminology Criteria for Adverse Events (CTCAE) version 4.0* unless otherwise specified ← ←			
CTCAE System/Organ/Class (SOC)	ADVERSE EVENT	AGENT	ACTION
Days 1-42			
Investigations	Platelet count decreased ≥ Grade 3		Omit lenalidomide (interrupt dose). Omit anti-coagulant or Aspirin while platelet count <50 x 10 ⁹ /liter. May re-initiate when platelet count >75 x 10 ⁹ /liter (must re-initiate at time lenalidomide restarted). Recheck CBC with platelet count weekly. If platelet count increases to >75 x 10 ⁹ /liter, decrease lenalidomide by 1 dose level and restart treatment. If platelet count does not increase to >75 x 10 ⁹ /liter by Day 35, discontinue lenalidomide.

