Appendix V
PATIENT MEDICATION DIARY

Patient Instructions

- Take at the same time each day with or without food.
- Please indicate on the calendar below *every* day that you take your study medication by placing the dose taken on the line under the date.
- If you miss a dose, place a check “0” under the date, but remember to take your prescribed dose at the next regularly scheduled time.
- Bring *all* bottles and any unused study medication along with this diary when you return for your next appointment.
- Lenalidomide capsules should be swallowed whole, and should not be broken, chewed or opened.

Medication(s)	Dose
Lenalidomide	Days 1-14: 2.5 mg Days 15-42: 5 mg (unless dose is reduced due to adverse events)

Study Drug	Day 1	Day 2	Day 3	Day 4	Day 5	Day 6	Day 7
Date							
Lenalidomide							

Study Drug	Day 8	Day 9	Day 10	Day 11	Day 12	Day 13	Day 14
Date							
Lenalidomide							

Study Drug	Day 15	Day 16	Day 17	Day 18	Day 19	Day 20	Day 21
Date							
Lenalidomide							

Study Drug	Day 22	Day 23	Day 24	Day 25	Day 26	Day 27	Day 28
Date							
Lenalidomide							

Study Drug	Day 29	Day 30	Day 31	Day 32	Day 33	Day 34	Day 35
Date							
Lenalidomide							

Study Drug	Day 36	Day 37	Day 38	Day 39	Day 40	Day 41	Day 42
Date							
Lenalidomide							

Date: _____ Participant’s Signature _____

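### Minor safety point, cheap to fix: Arm A steps up to 5 mg on calendar Day 15, but the first scheduled on-treatment blood count may come as late as Day 18

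*Combined protocol and SAP*

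**What the plan says.** All references are to the combined protocol and SAP.

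- **Dose step.** Section 7.1 gives Arm A 2.5 mg on Days 1-14 and 5 mg on Days 15-42. Section 8.1 repeats this for the starting level, with "5 mg p.o once daily" in the Days 15-42 column. The reduced levels also rise at Day 15; level -2, for example, begins at "2.5 mg p.o. Mondays and Thursdays". The diary the patient takes home (Appendix V) reads "Days 15-42: 5 mg (unless dose is reduced due to adverse events". The only qualifier in 7.1 is a pointer to section 8.0 for reductions after adverse events.
- **First on-treatment check.** In section 4.0 the row "CBC with differential and reticulocytes" is marked before registration, at the Day 15 visit, at Day 43 and at observation. Adverse events are first assessed on treatment at the same Day 15 visit. Section 7.2 sets the window: "the patient must return to the consenting institution for evaluation on Day 15 (+/-3 days".
- **Entry count.** Section 3.17: "The following laboratory values obtained ≤ 14 days prior to registration". Section 6.17: "Treatment cannot begin prior to registration and must begin ≤ 21 days after registration".
- **What a low count triggers.** Under section 8.2, "Platelet count decreased ≥ Grade 3" means lenalidomide is interrupted, with weekly rechecks and a lower level on restart. The neutrophil rule has the same form.

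**The concern.** The step is tied to a date, while the check that would stop it is tied to a visit that may come up to three days later. The adverse-event qualifier in 7.1 cannot act on a laboratory fall that nobody has measured. A patient who follows the diary and is seen on Days 16 to 18 doubles the dose at home. If platelets or neutrophils have already reached Grade 3, that patient is taking 5 mg when 8.2 would have required none.

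Section 15.191 describes myelosuppression as dependent on dose and reversible when drug is interrupted or reduced, so a fall is better found before the dose doubles than after. The neutrophil margin can also be thin: entry allows exactly 1000/mm³ (3.17), while 8.2 requires more than 1.0 x 10⁹/L, the same figure in other units, before drug is restarted. Section 11.2 says the study is not meant to treat the underlying leukemia, so there is little reason to accept avoidable exposure.

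**Working it through.** The plan gives no figure of its own on this point, so the check is calendar and dose arithmetic. Day 1 is taken as the first dose, with visits counted from it.

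**1. Visit window** (4.0, 7.2). 15 - 3 = Day 12; 15 + 3 = Day 18.

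**2. Doses at 5 mg before the count, starting level.** For a visit on Day v, the doses taken before the visit day number v - 15. Add one if the visit-day dose is taken before the blood draw. Each exceeds the earlier dose by 5 - 2.5 = 2.5 mg.

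| Visit day | 5 mg doses before visit day | With visit-day dose | Excess (mg) |
|---|---|---|---|
| 12-14 | 0 | 0 | 0 |
| 15 | 0 | 1 | 0 or 2.5 |
| 16 | 1 | 2 | 2.5 or 5 |
| 17 | 2 | 3 | 5 or 7.5 |
| 18 | 3 | 4 | 7.5 or 10 |

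**3. Cumulative drug before the count, visits on Days 16-18.** Days 1-14 contribute 14 x 2.5 = 35 mg.
- As written: 35 + 1 x 5 = 40 mg, up to 35 + 4 x 5 = 55 mg.
- If the step waits: 35 + 1 x 2.5 = 37.5 mg, up to 35 + 4 x 2.5 = 45 mg.
- Reduction: 2.5/40 = 6.3%, up to 10/55 = 18.2%.

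**4. Age of the entry count on Day 15 for a patient not yet seen.** Age = (days from count to registration) + (days from registration to Day 1) + 14.
- Dosing starts at registration: 0 + 0 + 14 = 14 days, up to 14 + 0 + 14 = 28 days. Section 1.5 places vaccination about two weeks after registration. Since vaccination is on Day 15, this puts Day 1 near registration.
- Both limits used in full: 14 (3.17) + 21 (6.17) + 14 = 49 days.
- If the step waits and review is on the visit day: 15 - 12 = 3 days for a Day 12 visit, and 0 days for visits on Days 15 to 18.

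**5. Reduced levels** (8.1). Level -1 goes from 2.5/2 = 1.25 to 2.5 mg per day on average. Level -2 goes from 2 x 2.5 = 5 to 3.5 x 2.5 = 8.75 mg per week. Any rule therefore has to be written by dose level.

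**6. Exposure given up by waiting.** Planned total: 35 + 28 x 5 = 175 mg. A Day 18 visit with same-day review loses 3 x 2.5 = 7.5 mg (7.5/175 = 4.3%), or 4 x 2.5 = 10 mg (10/175 = 5.7%) if the visit-day dose is also at the lower level. That leaves at least 28 - 4 = 24 days at 5 mg.

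**7. What stays uncovered.** From the Day 15 visit to the Day 43 visit (+/-4 days) is (43 - 4) - 18 = 21 to (43 + 4) - 12 = 35 days, with no scheduled count.

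**The case against.** The best reply is that the concern reads one table two ways. Section 7.1 puts both the dose step and the vaccine on Day 15. If that day is strict, the patient is in clinic then and the count is drawn; if it is nominal, the step can move with the visit. This would be a fair reading for a site to adopt. But the protocol gives the visit a window and the drug none, and the diary gives the patient plain dates. The gap is therefore permitted, though not inevitable.

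Second, other sources may supply a hold. Section 15.18 limits supply to one cycle under the REMS program, 15.1 refers to the Investigator's Brochure and package insert, and 15.191 asks for regular blood counts. The two sections that can be read in full set no hold and no date. The outside sources are not in the documents, so the claim is about the protocol text only.

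Third, a reader might infer more than the documents support:

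- *That counts are typically seven weeks old.* The 49 days needs both limits used in full, and section 1.5 makes that unlikely.
- *That patients on reduced levels are equally unprotected.* A patient reduced for a platelet or neutrophil fall already has weekly rechecks under 8.2. A note after the 8.2 table also keeps a reduced dose lowered through Day 42.
- *That the protocol raises the dose over a known cytopenia.* It does not; 8.2 governs once a count is known.

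Fourth, the benefit is small beside the 21 to 35 days at the higher dose with no scheduled count. That is true and limits the weight of the point, but it is no reason to leave a nearly free correction undone.

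**Conclusion.** The point holds as a minor patient-safety improvement. The protocol permits one to three doses at 5 mg, four with the visit-day dose, before any scheduled on-treatment count in patients seen on Days 16 to 18. The excess is 2.5 to 10 mg per patient at the starting level. The last scheduled count is then the entry one, roughly 14 to 28 days old on the expected timetable and 49 days at the limits.

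This rests on Day 1 being the first dose. The 7.1 table and the diary support that, but 7.2 counts days of the study without defining them. The documents give no visit-timing rates and no cytopenia rates for two weeks at 2.5 mg, so the number of patients affected cannot be estimated.

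It would be wrong to infer that the results are at risk. The primary comparison is of vaccine response, and section 16.323 tabulates the maximum grade per patient by arm, not by dose step. No planned analysis changes.

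**What to change.** Replace the 7.1 footnote on the 5 mg dose, and refer the Days 15-42 column heading in 8.1 to it for all three levels:

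> The Days 15-42 dose for the patient's dose level starts on the later of Day 15 and the day the Day 15 visit CBC and AE assessment have been reviewed against 8.2; until then the Days 1-14 dose for that level continues, subject to 8.2. If the visit or result is not available by Day 18, the site obtains a CBC promptly and the dose is not raised until it is reviewed. Waiting for this review is not a major violation under 13.5.

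Change the Appendix V dose line to:

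> Days 1-14: 2.5 mg (or your reduced dose). From Day 15: stay on your current dose until the study team tells you to change to your next dose (5 mg unless reduced); last dose Day 42.

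Leave the visit window, the vaccination day and the pre-vaccine draw as they are in both arms.

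**Cost.** One footnote, one heading reference and one diary line. No visit or test is added to the schedule; a missed visit or lost result may prompt one extra count. Late-seen patients have up to three or four fewer days at 5 mg with same-day review, and more if review is delayed. The change lowers but does not remove drug exposure before the first count, adds no count between the Day 15 visit and Day 43, and helps only patients still to be treated.

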8.0 Dosage Modification Based on Adverse Events

Strictly follow the modifications in this table. If multiple adverse events are seen, administer dose based on greatest reduction required for any single adverse event observed.

ALERT: *ADR reporting may be required for some adverse events (See Section 10)*

8.1 ARM A: Dose Levels (Based on Adverse Events in Tables 8.2).

Dose Level	Lenalidomide Days 1-14	Lenalidomide Days 15-42
0	2.5 mg p.o. once daily	5 mg p.o once daily
-1	2.5 mg p.o. every other day	2.5 mg p.o. once daily
-2	2.5 mg p.o. Mondays and Thursdays	2.5 mg p.o. every other day

* Dose level 0 refers to the starting dose.

8.2 Lenalidomide Dose Modifications

→ → Use the NCI Common Terminology Criteria for Adverse Events (CTCAE) version 4.0* unless otherwise specified ← ←			
CTCAE System/Organ/Class (SOC)	ADVERSE EVENT	AGENT	ACTION
Days 1-42			
Blood and lymphatic system disorders	Anemia ≥ Grade 3		Transfuse red blood cells at physician discretion. Continue current dose level. For repeat episodes of anemia related to lenalidomide, dose may be reduced at physician's discretion.
	Anemia ≤ Grade 2		Transfuse red blood cells at physician discretion. Continue current dose level.
Cardiac disorders	Sinus bradycardia or Ventricular arrhythmia Grade 2		Omit lenalidomide (interrupt dose). Re-evaluate toxicity weekly. When symptoms resolve to ≤grade 1, decrease lenalidomide by 1 dose level and restart lenalidomide at the discretion of the treating physician. If symptoms do not resolve to ≤grade 1 by Day 35, discontinue lenalidomide treatment.
	Sinus bradycardia or Ventricular arrhythmia ≥Grade 3		Discontinue lenalidomide treatment.
Endocrine disorders	Hyperthyroidism ≥ Grade 2		Omit lenalidomide (interrupt dose). Initiate appropriate therapy. Reassess in 2 weeks. If symptoms resolve to ≤grade 1 decrease lenalidomide by 1 dose level and resume treatment. If symptoms do not resolve to ≤grade 1 by Day 35, discontinue lenalidomide.
	Hypothyroidism ≥ Grade 2		Omit lenalidomide (interrupt dose). Initiate appropriate therapy for hypothyroidism. Reassess in 2 weeks. If symptoms resolve to ≤grade 1 decrease lenalidomide by 1 dose level and resume treatment. If symptoms do not resolve to ≤grade 1 by Day 35, discontinue lenalidomide.

→ → Use the NCI Common Terminology Criteria for Adverse Events (CTCAE) version 4.0* unless otherwise specified ← ←			
CTCAE System/Organ/Class (SOC)	ADVERSE EVENT	AGENT	ACTION
Days 1-42			
Investigations	Platelet count decreased ≥ Grade 3		Omit lenalidomide (interrupt dose). Omit anti-coagulant or Aspirin while platelet count <50 x 10 ⁹ /liter. May re-initiate when platelet count >75 x 10 ⁹ /liter (must re-initiate at time lenalidomide restarted). Recheck CBC with platelet count weekly. If platelet count increases to >75 x 10 ⁹ /liter, decrease lenalidomide by 1 dose level and restart treatment. If platelet count does not increase to >75 x 10 ⁹ /liter by Day 35, discontinue lenalidomide.
	Neutrophil count decreased ≥ Grade 3		Omit lenalidomide (interrupt dose). Recheck neutrophil count weekly. If neutrophil count > 1.0 x 10 ⁹ /liter, decrease lenalidomide by 1 dose level and restart treatment. If neutrophil count does not increase to > 1.0 x 10 ⁹ /liter by Day 35, discontinue lenalidomide. Growth factor support may be administered at the discretion of the treating physician. See Section 9.2.
Neoplasms benign, malignant and unspecified (incl cysts and polyps)	Tumor pain ≥ Grade 3		Note: Differentiate tumor flare from disease progression. Treat with naproxen 500 mg p.o. BID. Continue lenalidomide during flare reaction. If patient does not experience adequate relief after 2 days of naproxen, add prednisone 20 mg p.o. daily. Steroids should be tapered as tolerated at the discretion of the treating physician.

→ → Use the NCI Common Terminology Criteria for Adverse Events (CTCAE) version 4.0* unless otherwise specified ← ←			
CTCAE System/Organ/Class (SOC)	ADVERSE EVENT	AGENT	ACTION
Days 1-42			
Nervous system disorders	Peripheral motor neuropathy or Peripheral sensory neuropathy Grade 3		Omit lenalidomide (interrupt dose). Re-evaluate toxicity weekly. When symptoms resolve to ≤grade 1, decrease lenalidomide by 1 dose level and resume treatment. If symptoms do not resolve to ≤grade 1 by Day 35, discontinue lenalidomide.
	Peripheral motor neuropathy or Peripheral sensory neuropathy Grade 4		Discontinue lenalidomide
Skin and subcutaneous tissue disorders	Rash maculo-papular Grade 3		Omit lenalidomide (interrupt dose). Initiate supportive care measures as appropriate. Re-evaluate toxicity weekly. When symptoms resolve to ≤grade 1, decrease lenalidomide by 1 dose level and resume treatment. If symptoms do not resolve to ≤grade 1 by Day 35, discontinue lenalidomide.
	Stevens-Johnson syndrome ≥ Grade 3		Discontinue lenalidomide
	Erythema multiforme ≥ Grade 3		Discontinue lenalidomide.
Vascular disorders	Thromboembolic event ≥ Grade 3		Discontinue lenalidomide. Initiate anti-coagulation as appropriate.
Other non-hematologic	≥ Grade 3 as per NCI Common Terminology Criteria for Adverse Events v4.0 that does NOT respond to supportive care measures		Omit lenalidomide (interrupt dose). Re-evaluate toxicity weekly. When symptoms resolve to ≤grade 1, decrease lenalidomide by 1 dose level and restart treatment at the discretion of the treating physician. If symptoms do not resolve to ≤grade 1 by Day 35, discontinue lenalidomide treatment.

- 8.3 Plevnar 13 will be given per protocol regardless of whether or not lenalidomide dose reduced or omitted.

* Located at http://ctep.cancer.gov/protocolDevelopment/electronic_applications.ctc.htm

NOTE: If the patient experiences a significant adverse event requiring a dose reduction, then the dose will remain lowered through day 42.

NOTE: Adverse events requiring a dose-reduction step for lenalidomide beyond the two dose-reduction steps (levels -1 and -2) will be at the discretion of the treating physician, if the decision is made for the patient to be kept on study. These dose reductions must be clearly recorded in reported clinical data.

